#### 6.1.2 Inclusion criteria

Non-hospitalised individuals aged 18 years and over with a SARS CoV-2 RT-PCR result in SGSS data linked to CPRD Aurum, and willing to provide informed consent and to undertake the protocol activities.

#### 6.1.3 Exclusion criteria

Individuals without a positive SARS CoV-2 RT-PCR test result in CPRD Aurum.

Individuals with a hospital admission within 28 days of a positive SARS CoV-2 RT-PCR result in CPRD AURUM.

Individuals aged under 18 years.

Individuals unable/unwilling to provide informed consent.

Individuals unable/unwilling to undertake the protocol activities.

Individuals deemed appropriate for exclusion by their GP (e.g., on a palliative care register).

## **6.2 Matched controls - Group 1 (minimum of 500 participants)**

### **6.2.1 Eligibility Criteria**

Propensity score-matched individuals without a diagnosis of COVID-19 (suspected or confirmed) in CPRD Aurum and without a positive SARS CoV-2 RT-PCR result in linked SGSS data and without a record of hospital admission within 28 days of the index date will comprise Control Group 1. For propensity score matching we will use covariates such as sociodemographic characteristics, lifestyle and metabolic profile measures and presence of comorbidities, especially those identified as risk factors for COVID-19.

### **6.2.2 Inclusion criteria**

Individuals aged 18 years or over without a diagnosis of COVID-19 (suspected or confirmed) in CPRD Aurum and without a positive SARS CoV-2 RT-PCR result in linked SGSS data and able to provide informed consent and undertake the protocol activities.

### **6.2.3 Exclusion criteria**

Individuals with a diagnosis of COVID-19 in CPRD Aurum or positive SARS CoV-2 RT-PCR result in SGSS.

Individuals coded in their primary care record as having suspected COVID-19.

Individuals aged under 18 years.

Individuals unable or unwilling to provide informed consent.

Individuals unable or unwilling to undertake the protocol activities.

Individuals deemed appropriate for exclusion by their GP (e.g., on a palliative care register).

## **6.3 Matched controls - Group 2 (50 participants)**

### **6.3.1 Eligibility criteria**

Participants taking part in the study who have had a positive SARS CoV-2 RT-PCR test result in SGSS data linked to CPRD but not reporting symptoms on ATOM5™ beyond 12 weeks from the positive RT-PCR test result will comprise Control Group 1. These control participants will be propensity score-matched to participating Long COVID patients.

### **6.3.2 Inclusion criteria**

Participants taking part in the study who have had a positive SARS CoV-2 RT-PCR test result in SGSS data linked to CPRD but not developed Long COVID symptoms based on the data reported in ATOM5 and able to provide informed consent and to undertake the protocol activities.

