Patients with COVID-19 will be propensity score matched to patients without a COVID-19 diagnosis (minimum n=500), who will similarly be invited to participate in the study following eligibility checking by their general practice. This will constitute control group 1. Propensity scores will be estimated for the likelihood of COVID-19 using logistic regression, including the following data obtained from CPRD Aurum: age, sex, socio-economic status, body mass index (BMI), smoking status, comorbidities and risk factors for COVID-19 identified by Public Health England. A second control group of at least 500 participants will be derived from those with COVID-19 who do not report long-term symptoms (i.e., do not have Long COVID).

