### **Second-Generation Surveillance System (SGSS)**

SGSS is the national laboratory reporting system used in England to capture routine laboratory data on infectious diseases and antimicrobial resistance. The SARS-CoV-2 testing started in UK laboratories on 24/02/2020, with the SGSS data reflecting testing (swab samples, PCR test method) offered to those in hospital and NHS key workers (i.e., Pillar 1). The linked SGSS data only contains positive tests results. The primary care data itself includes both positive and negative Pillar 2 PCR and other RNA detection COVID-19 test results and it is estimated that over 80% of all such tests undertaken in England are being matched to GP records.

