## 8.0 Study procedures

### 8.1 Population-based representative cohort of individuals with long COVID and matched controls

Eligible individuals who wish to participate will download the Aparito Atom5™ app or visit the website and register using their unique one-time use on-boarding code. They will then be asked to provide electronic consent on the app or website, which includes confirming that participants with a positive SARS CoV-2 RT-PCR result have not been hospitalised within 28 days of being diagnosed with COVID-19. Control participants will be asked if they have ever had COVID-19 to check eligibility for inclusion as a control subject. Once the consent form has been completed, participants will be asked to complete a brief demographic and clinical questionnaire. The questionnaire will ask for the following details: name, sex, date of birth, contact number, postal address, ethnic group, GP address, height, weight, smoking status, pregnancy status, SARS CoV-2 vaccination status, confinement (shielding) status, care home residence, occupation, occupational status (in work, furlough, etc.), and over-the-counter medications used to manage symptoms. Full details of these questions are provided in the appendix (Baseline data collection in Atom5™) and in Table 1.0.

Participants will then be invited to report the presence of established Long COVID symptoms and quality of life using validated tools at monthly intervals for a period of 12 months. At each time point, participants will be asked to confirm their willingness to continue to participate in the study. Those wishing to withdraw will be asked to complete a withdrawal form and advised that any data collected up to that point will need to be retained as it will have been used in aggregated data analyses.

As requested by our PPI group, we will ensure that people who are unable to use the app or website (due to no access to a smartphone or internet connection, patient preference, language, or other requirements) can participate through nurse interview-led appointments (telephone or video conference) with translators as required. Information and contact numbers will be provided on the PIS. Alternative language versions of each PRO will be provided where validated translations exist (see table below) The translated questionnaires are currently being programmed on the app.

	English	Bengali	Polish	Welsh	Punjabi	Gujarati	Urdu
EQ5D5L	X	X	X	X	X	X	X
FACIT F	X	X	X		X	X	X
PHQ-2	X	X	X		X	X	
GAD-2	X		X		X	X	X

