Participants will complete the questionnaires monthly within a timeframe window of -/+ 7 days. Reminders/notifications will be sent by Atom5™ at Baseline/+2 days/+6 days for the baseline questionnaires and at -7 days/0/+2 days for subsequent ones.

At registration, all participants will be asked to provide the onboarding code provided in their invitation letter. Once participants have registered and provided informed consent, they will then be invited to provide baseline demographic data and report the presence of a wide range of symptoms, quality of life and work/education capability using validated tools via the Atom5™ platform.

Patient-reported outcomes will be assessed using symptom specific measures (Table 1): Symptom Burden Questionnaire-Long COVID (SBQ-LC™), FACIT-Fatigue, modified MRC Dyspnoea Scale, COVID-19 core outcome measure for recovery, Patient Health Questionnaire-2 (PHQ-2), Generalized Anxiety Disorder-2 (GAD-2), Abbreviated PTSD Checklist (PCL-2), and quality of life using the EuroQol-5D (EQ-5D).

The SBQ-LC™ will undergo further validation during the study. The development and initial validation of SBQ-LC™ has been applied for through a separate ethics application to the University of Birmingham Research Ethics Committee since participants will not be recruited via the NHS. The SBQ is a disease-specific, multi-domain instrument that will be used to assess symptom burden and functional status (interference). Respondents will be asked to indicate the presence of a symptom over the last 7 days and then provide an indication of symptom burden by providing a response on a 5-point ordinal scale measuring either symptom severity, symptom frequency, or interference. Higher scores will be indicative of greater symptom burden and interference.

The Functional Assessment of Chronic Illness Therapy –Fatigue Scale (FACIT-Fatigue) is a 13-item measure that assesses self-reported fatigue and its impact upon daily activities and function. It has been validated for use across a range of populations. The FACIT-Fatigue has a 7-day recall period and is scored on a 5-point Likert Scale from “0-Not at all” - to “4-Very much”. Individual items scores are summed (two items of which are reverse scored), multiplied by 13 and then divided by the number of items answered, with a higher score indicating less fatigue and better quality of life. It takes less than 5 min to complete.

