The modified MRC Dyspnoea Scale is a modification to the widely used MRC Dyspnoea scale. The item has a 24-hour recall period and is scored on a 5-point Likert scale from “0 - I only get breathless with strenuous exercise” to “4 - I was breathless when dressing, talking or at rest”. It has a high degree of conceptual overlap with its parent clinical measure, the MRC Dyspnoea scale, which is in wide-scale clinical practice.

The COVID-19 core outcome measure for recovery is a single item intending to measure a return to the pre-illness state. The item has a same day recall period and is scored on a 5-point Likert scale from “0 - Completely recovered” to “5 - Not recovered at all”.

The Euroqol EQ-5D-5L comprises five items plus one visual analogue scale. It has been widely validated and used to assess health outcomes from a wide variety of interventions on a common scale for purposes of evaluation, allocation and monitoring. It is used by the National Institute for Health and Care Excellence (NICE) in health technology assessment. EQ-5D-5L takes only a few minutes to complete and has a same day recall period.

The GAD-2 is a screening tool for generalised anxiety disorder derived from the GAD-7. It comprises the first 2 items of the GAD-7, which are considered as the core anxiety symptoms (“feeling nervous, anxious or on edge”/Not being able to stop or control worrying”). The GAD-2 performs well as a screening tool for three other common anxiety disorders (panic disorder, social anxiety disorder, and PTSD). It has a recall period of two weeks. The GAD-2 has a global score (0-6, no weighting). A higher score indicates an increased likelihood of underlying anxiety disorder. The recommended cut-off score for further investigation is  $\geq 3$ . The GAD-2 has been validated in many studies and has retained the same psychometrics properties of the GAD-7 (86% sensitivity/83% specificity)

The PHQ-2 is a screening tool for depression derived from the PHQ-9. It comprises the first 2 items of the PHQ-9 (depressed mood and anhedonia). The PHQ-2 has a recall period of 2 weeks. It has a global score (0-6, no weighting). A higher score indicates an increased likelihood of an underlying depressive disorder. The recommended cut-off score for further investigation is  $\geq 3$ . The PHQ-2 has been validated in many studies and has shown a sensitivity of 83% and specificity of 92%.

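### Control Group 2 is defined by Atom5 reports alone, so it selects people with no current Long COVID symptoms rather than people who never developed Long COVID

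*Protocol*

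**What the plan says.** Section 6.3.1 takes participants with a positive RT-PCR result "but not reporting symptoms on ATOM5™ beyond 12 weeks from the positive RT-PCR test result". (Its text calls them Control Group 1, but the heading and the rest of the protocol make clear that Control Group 2 is meant.) Section 6.3.2 describes the same people as having had a positive test "but not developed Long COVID symptoms based on the data reported in ATOM5 and able to provide informed consent". The WP1 text in section 5.0 likewise treats not reporting long-term symptoms as not having Long COVID. The exclusions in 6.3.3 cover consent, ability to take part and GP judgement. They do not mention past Long COVID.

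Reporting begins after registration. Under section 8.1 participants "report the presence of established Long COVID symptoms and quality of life using validated tools at monthly intervals" for 12 months. For the SBQ-LC, "Respondents will be asked to indicate the presence of a symptom over the last 7 days" (section 9.1). Of the COVID-19 recovery measure, the same section says: "The item has a same day recall period and is scored on a 5-point Likert scale". The longest look-back among the listed instruments is one month, for the PCL-2.

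On timing, Box 1 says: "The SARS-CoV-2 testing started in UK laboratories on 24/02/2020". The version log dates this protocol 05/07/2021. Sections 6.1 and 6.3 set no maximum interval between the positive test and enrolment.

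**The concern.** The label describes a history: this person did not develop Long COVID. The rule measures a present state: this person has reported no symptoms since joining Atom5. The two agree only if nobody had symptoms beyond 12 weeks that ended before registration.

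The protocol takes more care with Control Group 1. Section 6.2.3 excludes even suspected COVID-19 in the primary care record, and section 8.1 asks controls whether they have ever had COVID-19. The listed items contain no equivalent question on whether a PCR-positive participant ever had prolonged symptoms.

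Control Group 2 is one of two comparators for the autoantibody, T-cell, proteomic and sncRNA work, and for the description of health service use and mortality (section 5.0, WP2; section 11). A resolved case who still carries immune or protein changes, or who shares the risk factors or care pattern of Long COVID, makes the control group look more like the cases. An analysis plan cannot undo this if the history was never collected.

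**Working it through.** **1. Can a resolved case meet the rule?** From 24 February 2020 to 5 July 2021 is 497 days, or 71 weeks (about 16 months). Long COVID starts at week 12, so the earliest possible case could have resolved up to 71 − 12 = 59 weeks before enrolling on the version date. (Using the version date as the earliest enrolment under this text is an assumption.) Such a person has nothing to report in a 7-day, same-day or one-month window, and so meets 6.3.1 and 6.3.2. The 71 weeks is a maximum. The mechanism needs only a positive test well over 12 weeks before enrolment and recovery in between.

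**2. What share of Control Group 2 could this be?** Let s be the share of PCR-positive participants who ever had symptoms beyond 12 weeks, and r the share of those resolved before enrolment. The pool that reports no long-term symptoms is (1 − s) never affected plus s·r resolved, so the contaminated share is

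c = s·r / (1 − s + s·r).

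Inputs: s = 10%, from the statement in section 1.0 that symptoms persist in up to 10%. The documents give no r, so 30-70% is assumed.

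| r | c | Of 50 BioWear controls |
|---|---|---|
| 30% | 0.03/0.93 = 3.2% | 1.6 |
| 50% | 0.05/0.95 = 5.3% | 2.6 |
| 70% | 0.07/0.97 = 7.2% | 3.6 |

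**3. What would that do to the BioWear comparison?** Table 3 gives power for a Kruskal-Wallis test of 50 against 50. Simulation (20,000 replicates, alpha 0.05) reproduces all ten t5 rows and nine of the ten normal rows within 2 points. The remaining row, d = 0.6 normal, is stated as 80.8% and came out at 82.8% and 82.3% in two runs, which is borderline.

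Now give each control the full case shift with probability c. This is the worst case: resolved cases are biologically identical to current ones. The mean difference shrinks from d to (1 − c)·d. At d = 0.6 it becomes 0.6 × 0.968 = 0.58 for c = 3.2%, and 0.6 × 0.928 = 0.56 for c = 7.2%.

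| c | Power at d = 0.6, normal | Power at d = 0.6, t5 |
|---|---|---|
| 0 | 82% | 72% |
| 5% | 78% | 67% |
| 10% | 74% | 62% |

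The 3-7% range lies between the first and last rows. If resolved cases keep only part of the shift, the loss is smaller.

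**The case against.** **The baseline form is not shown.** Section 8.1 refers to an appendix for the full baseline questions. The two lists that can be read, in section 8.1 and Table 1.0, are incomplete: section 5.0 says participants will be asked about comorbidities, and neither list has that item. A history question could therefore exist. This stands and lowers confidence that the item is missing. It does not rescue the rule, because 6.3.1 and 6.3.2 do not say that pre-enrolment history counts.

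**Symptom comparisons are not affected in the same way.** A reader might infer that the additional symptom burden of Long COVID, or the known-groups and ROC analyses of the SBQ-LC, are pulled toward the null. That does not follow: resolved cases have few current symptoms and score like other controls. Nor does the protocol rank Control Group 2 as the main comparator. It uses both control groups and also compares syndromes, and contrasts with Control Group 1 or between syndromes are unaffected.

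**A larger figure is tempting but unsupported.** A reader might take 500 of 2000 as a 25% ever-affected share. Those are recruitment minima, and the 500 are people identified from Atom5 reports, so they are not everyone ever affected. If s were 25% and r 30-70%, only 2000 × 0.25 × (1 − r) = 350 to 150 people would report Long COVID, which contradicts the 500. The true share may be above or below 10%; these counts cannot settle it.

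**Extremes and mitigation.** Early tests came from hospital patients and NHS key workers, and admissions within 28 days are excluded, so very long intervals may be uncommon. Monthly reporting up to bio-sampling at 3 months (section 11.1) gives a relapsing course several chances to surface. This helps with relapse but cannot detect illness that has fully resolved.

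**The Long COVID arm.** One might add that it under-represents fast-resolving syndromes. Studying people with current symptoms follows from the aim of measuring symptom burden and clusters, so that is not pressed here.

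**Conclusion.** The point holds as a mismatch between label and rule. As written, Control Group 2 is people with no Long COVID symptoms reported since joining Atom5, and resolved Long COVID is allowed in. That conclusion comes from the text and needs no assumed figure.

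The consequence is possible dilution of the biomarker, risk-factor and health-service-use contrasts against this group. On the protocol's figure of up to 10%, with an assumed 30-70% resolved before enrolment, about 3-7% of the group is affected, roughly 2-4 of 50 sampled controls. In the worst case this costs Table 3 a few points of power, less than the 8 points (82% to 74%, normal, d = 0.6) seen at 10% contamination. A higher ever-affected share would raise it. The size is modest on these inputs, but the baseline history may not be recoverable later, which is the reason to settle it before Control Group 2 is matched and sampled. Confidence is moderate, because the baseline appendix is not shown.

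**What to change.** 1. Check the Atom5 baseline appendix. If it has no such item, add one for every PCR-positive participant on how long symptoms lasted after the positive test: under 4 weeks, 4-12 weeks, over 12 weeks but now resolved, or still present.
2. Reword 6.3.1 and 6.3.2 so that Control Group 2 requires no symptoms beyond 12 weeks at any time since the positive test, by history and by Atom5 follow-up. Align the WP1 text in section 5.0.
3. Report resolved Long COVID as its own category, outside Control Group 2 and its BioWear sample.
4. If history cannot be collected, relabel the group as having no current Long COVID symptoms and limit the conclusions accordingly.

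The cost is one question and a reworded rule. The history item will carry some recall error, and the control pool becomes slightly smaller, though it is drawn from a COVID-19 cohort of at least 2000.

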### **6.3.3 Exclusion criteria**

Participants unable/unwilling to provide informed consent.

Participants unable/unwilling to undertake the protocol activities.

Participants deemed appropriate for exclusion by their GP (e.g., on palliative care register).

## **6.4 Bio-sampling and wearables (BioWear) cohort (200 Long COVID participants, 50 participants from Control Group 1 and 50 participants from Control Group 2)**

### **6.4.1 Eligibility Criteria**

Participants in the study who have self-reported symptoms associated with COVID-19 more than 12 weeks since a positive SARS CoV-2 RT-PCR test or COVID-19 diagnosis. This will include 50 randomly sampled participants from each Long COVID symptom cluster, up to a maximum of 200 Long COVID participants. 50 participants randomly sampled from Control Group 1 and 50 participants randomly sampled from Control Group 2 will also be eligible.

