### 4.0 Research Outputs and Deliverables

[figure not shown]
1. To establish a population-based representative cohort of 4000 individuals (minimum 2000) with COVID-19, with a minimum of 500 individuals with Long COVID, 500 matched control patients without COVID-19 (control group 1) and 500 matched control patients with COVID-19 but without Long COVID (control group 2). We will capture detailed data on symptoms, quality of life, work capability and objective health measures for individuals with Long COVID and patients in the matched control groups. This will include the development and validation of a new disease-specific PRO of symptom severity and interference for individuals with Long COVID.
2. To develop a new, validated PRO for the measurement of symptom burden in individuals with Long COVID: the Symptom Burden Questionnaire™: Long COVID.

3. To describe distinct Long COVID syndromes and their epidemiology and characterise their immune, inflammatory and proteomic profile, and physical parameters (heart rate intensity, sleep and movement) providing mechanistic understanding of each syndrome and identifying potential therapeutic targets for future evaluation. This will accelerate the identification of potential therapies for Long COVID that are targeted to each syndrome. Based on symptom clusters we will identify up to 200 individuals from the Long COVID cohort, 50 matched control patients without COVID-19, and 50 matched control patients with COVID-19 but without Long COVID to receive bio-sampling and be provided with wearable devices (Garmin Vivosmart4) to measure heart rate, oxygen saturation, step count and sleep quality (BioWear Sub-Study). This will be used in WP2 to deep phenotype Long COVID syndromes.
4. To co-produce a targeted intervention for Long COVID syndromes that can be delivered remotely on a digital platform. This intervention will have patients and carers at the heart of its design and will be based on the best available evidence on Long COVID. It will be designed to be effective, targeted to address symptoms associated with each specific syndrome, acceptable to patients, and scalable.

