### **6.5.3 Bio-sampling and wearables (BioWear) sub-cohort**

Researchers will identify distinct symptom clusters (syndromes) using linked data from CPRD and data collected via the Atom5™ platform. A random sample of up to 300 participants (200 participants with Long COVID, with 50 sampled from each of the four most prevalent Long COVID syndromes, and 50 participants from each of the two control groups) who have previously consented to be contacted for bio-sampling will be identified and invited to take part in the BioWear sub-study. Selected participants will be sent an invitation to participate and the BioWear sub-study PIS via the Atom5™ app, SMS message or by post for those who have expressed having difficulty accessing digital platforms. Those individuals showing an interest in taking part will be contacted by a member of the research team to arrange a date and time for blood and saliva sample collection and to be provided with a wearable device (Garmin Vivosmart4).

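### The bio-sampling controls are called matched, but they are drawn at random from groups matched to other populations, and no step aligns them with the selected Long COVID participants.

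*Protocol*

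**What the plan says.** Item 3 of Section 4.0 promises "50 matched control patients without COVID-19, and 50 matched control patients with COVID-19 but without Long COVID to receive bio-sampling". The Study Summary uses the word matched only for the 50 controls without COVID-19. The immunological phenotyping text in Section 5.0 (Objective 5, part A) again speaks of two matched control sets.

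The operative rules are in 6.4.1 and 6.5.3. For controls, 6.4.1 says "50 participants randomly sampled from Control Group 1 and 50 participants randomly sampled from Control Group 2 will also be eligible". For cases it says "This will include 50 randomly sampled participants from each Long COVID symptom cluster, up to a maximum of 200 Long COVID participants". Section 6.5.3 repeats the scheme as a random sample, "with 50 sampled from each of the four most prevalent Long COVID syndromes, and 50 participants from each of the two control groups", restricted to people who agreed to be contacted. Sections 11.1 and 14.2 add no matching step.

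The parent groups were matched as follows.
- **Control Group 1** (Section 5.0, Objective 1): "Patients with COVID-19 will be propensity score matched to patients without a COVID-19 diagnosis (minimum n=500"), and "Propensity scores will be estimated for the likelihood of COVID-19 using logistic regression".
- **Control Group 2** (6.3.1): "These control participants will be propensity score-matched to participating Long COVID patients".

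**The concern.** A matched control group is balanced only against the population it was matched to. Here that population is not the sampled Long COVID group for either set of controls, and nothing in the sampling rule corrects this.

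The protocol itself gives the reason for care. Section 2.0 reports that Long COVID is more frequent in women, in older adults and with particular symptom clusters, and that older adults with COVID-19 have more senescent T cells. Section 5.0 then makes senescent T cells a target, compared across the syndromes and both control sets. If the sampled Long COVID participants are older than Control Group 1, an unadjusted comparison would tend to show more senescence in Long COVID even if Long COVID had no effect on it. A reader told that the controls are matched would not look for this.

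**Working it through.** **1. The plan's own figure.** Table 3 (Section 14.2) gives the power of a Kruskal-Wallis test for 50 v 50 at alpha 0.05. Simulation with two independent samples, a location shift d and 20,000 replicates per cell gives:

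| d | Table 3, normal / t5 | Simulated, normal / t5 |
|---|---|---|
| 0.5 | 66.3% / 56.2% | 67.9% / 57.0% |
| 0.6 | 80.8% / 71.7% | 82.6% / 72.2% |
| 0.8 | 95.8% / 92.5% | 97.0% / 92.3% |

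All 20 cells agree within 2 points. Table 3 is therefore sized for unpaired samples without covariates. It relies on no pairing, and it makes no allowance for a covariate difference between the groups.

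**2. Matching target against comparison group.**

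| Controls | Matched to | Compared with |
|---|---|---|
| Group 1 | all COVID-19 patients, on likelihood of COVID-19 | up to 200 Long COVID participants, 50 per syndrome |
| Group 2 | participating Long COVID patients as a whole | the same |

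Under 6.5.2, the Control Group 1 list is drawn from the primary care database before invitation. Long COVID status becomes known only from app data after enrolment (6.5.1, on recruitment). So Group 1 could not have been matched to Long COVID participants.

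**3. Shift from equal allocation (bears on Control Group 2).** Let p_k be the share of syndrome k in the Long COVID cohort, m_k its mean on a covariate in SD units, and n_k the number sampled.

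Shift = Σn_k·m_k / Σn_k − Σp_k·m_k

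The protocol gives neither p_k nor m_k, so both are assumed here. With m_k evenly spaced over the span shown and 50 sampled per syndrome:

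| Shares (%) | span 0.2 SD | span 0.5 SD | span 0.8 SD |
|---|---|---|---|
| 25/25/25/25 | 0 | 0 | 0 |
| 40/30/20/10 | 0.03 | 0.08 | 0.13 |
| 55/25/12/8 | 0.05 | 0.13 | 0.21 |

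The extreme cases are limited by numbers. With 8% of a cohort of 500 there are only 40 people. Taking all 40 gives (50×0 + 50×0.267 + 50×0.533 + 40×0.8)/190 = 72/190 = 0.379, against a cohort mean of 0.195, so the shift is 0.18.

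A steeper case, with shares 55/25/15/5% and means 0, 0.2, 0.5 and 0.8, would give 0.375 − 0.165 = 0.21 if every syndrome supplied 50. A 5% syndrome holds 25 of 500, so the sample mean is 55/175 = 0.314 and the shift is 0.15. With 37 available out of 750 it is 64.6/187 − 0.165 = 0.18. A fair range is 0 to roughly 0.15–0.2 SD.

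**4. What a gap does to an unadjusted test.** Bias in the biomarker, in SD units, equals the covariate gap times the covariate–biomarker correlation. The gaps and correlations are assumed; the rates come from the same simulation with normal data and no true difference.

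| Gap (SD) | Correlation | Bias (SD) | False positives, 50 v 50 | 50 v 200 |
|---|---|---|---|---|
| 0.2 | 0.3 | 0.06 | 5.9% | 6.6% |
| 0.2 | 0.5 | 0.10 | 7.5% | 9.2% |
| 0.5 | 0.3 | 0.15 | 11.0% | 14.9% |
| 0.5 | 0.5 | 0.25 | 22.9% | 33.2% |

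On these assumptions the Control Group 2 shift alone takes a 5% test to at most about 8% (50 v 50) or 9% (50 v 200). For Control Group 1 the gap cannot be calculated from the protocol, so the lower rows are illustrations, not estimates.

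**The case against.** **Matched is a label.** The headings of 6.2 and 6.3 use it as the name of the two parent groups, so 50 matched controls may mean 50 people from those groups, which is what 6.4.1 delivers. No section promises individual re-matching. This is fair as to wording. It does not help Control Group 1, whose matching was never to Long COVID participants.

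**A random draw keeps the parent group's distribution in expectation.** This stands. The draw alone is not the fault; the fault is that the parent distribution is not that of the sampled cases.

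**Stronger readings a reader might infer, which the protocol does not support.**
- *Chance imbalance.* At 50 v 50 the SD of a standardised difference is √(1/50 + 1/50) = 0.20, so one covariate exceeds 0.2 in 32% of draws, and at least one of six independent covariates in about 90%. This would hold between any two random groups of 50. The test's alpha already allows for it, and it is not bias.
- *Broken pairs.* If matching were 1:1 with full uptake, only about 50×200/500 = 20 (cohort of 500) or 50×200/750 = 13 (cohort of 750) of the 50 Group 2 controls would keep a partner among the 200. No paired analysis is planned, so this has no consequence.
- *Matching thrown away.* For Control Group 1 there was no matching to Long COVID to lose.

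**The analysis may adjust.** The statistical analysis plan was not available to this review and may adjust for age and sex. That would reduce the bias, but it would not make the controls matched or supply controls at ages where few were drawn.

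**Stratifying does not balance each syndrome.** This also stands. With evenly spaced syndrome means and 50 per syndrome, the most extreme syndrome lies half the span from the pooled mean: 0.10 to 0.40 SD for spans of 0.2 to 0.8.

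**Conclusion.** The point holds as one of systematic difference. The protocol calls the bio-sampling controls matched, yet no step aligns them with the Long COVID participants they are compared with, and age and sex are plausible confounders on its own account. For Control Group 2 the shift lies between 0 and roughly 0.15–0.2 SD under assumed syndrome shares and means; it is nil if the syndromes are of equal size or do not differ on the covariate. For Control Group 1 the size is unknown and no matching to Long COVID limits it. Restricting the draw to people who agreed to contact may move either side further, by an amount the protocol does not allow one to judge. The biomarker work is exploratory, so this is a moderate fault that should be corrected because the remedy is cheap and is available only before sampling.

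**What to change.** In 6.4.1 and 6.5.3, state that the Long COVID participants are selected first. Then draw the 50 controls from each control group at random within strata, at least age band by sex, with stratum numbers set to the distribution of the selected Long COVID participants. Call these controls frequency-matched on those factors in Section 4.0, the Study Summary and Section 5.0. If this is not done, drop matched for the sub-study. In either case, syndrome-level comparisons should be adjusted for age and sex.

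At the same time reconcile 6.3: its heading gives Control Group 2 as 50 participants, while the Study Summary, Section 5.0 and 6.5.2 give 500, and 6.3.1 labels it Control Group 1. A random draw of 50 has meaning only with the larger figure.

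The cost is a change to the sampling code and a sentence in each of the two sections. Date of birth and sex are already collected at baseline (Table 1.0), and no extra participants or visits are needed. Some strata may hold few consenting controls, so a rule for using the nearest stratum should be written down beforehand.
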